### 10.0 Reporting Requirements

### Safety Monitoring

The principal investigator is responsible for monitoring the safety of patients who enroll in the study. All adverse events (AEs) occurring after any administration of the study drug will be followed until resolution, stabilization, death, loss to follow up, or commencement of new therapy.

# 10.1 Serious Adverse Event (SAE) Reporting

### Adverse Event Definition

The CTEP active version of NCI Toxicity Criteria may be used by the Investigator as a guide in determining the severity of adverse events.

Clinically significant adverse events (AEs) and Serious Adverse Events (SAEs) occurring during the study that are thought to be related to Glutamine or Best Supportive Care should be documented in the medical record.

Toxicities of all grades that are felt to be related to Glutamine or Best Supportive Care, and all grades of mucositis, esophagitis, and weight loss will be documented in the patient electronic medical record. Unless otherwise documented in the electronic medical record as clinically significant and study drug related, all lab abnormalities will be assumed to be related to the patient's other co-morbid conditions, prior therapies, other concomitant therapies/medications, or underlying cancer. In this study, only adverse events related to the study drug, not related to mTOR inhibitor therapy or radiation therapy will be recorded.

# Serious Adverse Event (SAE)

- An adverse event or suspected adverse reaction is considered "serious" if, in the view of either the investigator or the sponsor, it results in any of the following outcomes:
- Death
- A life-threatening adverse drug experience any adverse experience that places the patient, in the view of the initial reporter, at immediate risk of death from the

adverse experience as it occurred. It does not include an adverse experience that, had it occurred in a more severe form, might have caused death.

- Inpatient hospitalization or prolongation of existing hospitalization
- A persistent or significant incapacity or substantial disruption of the ability to conduct normal life functions.
- A congenital anomaly/birth defect.

Important medical events that may not result in death, be life-threatening, or require hospitalization may be considered a serious adverse drug experience when, based upon appropriate medical judgment, they may jeopardize the patient or subject and may require medical or surgical intervention to prevent one of the outcomes listed in this definition. Examples of such medical events include allergic bronchospasm requiring intensive treatment in an emergency room or at home, blood dyscrasias or convulsions that do not result in inpatient hospitalization, or the development of drug dependency or drug abuse (21 CFR 312.32).

- Important medical events as defined above, may also be considered serious adverse events. Any important medical event can and should be reported as an SAE if deemed appropriate by the Principal Investigator or the IND Sponsor, IND Office.
- All events occurring during the conduct of a protocol and meeting the definition of a SAE must be reported to the IRB in accordance with the timeframes and procedures outlined in "The University of Texas M. D. Anderson Cancer Center Institutional Review Board Policy for Investigators on Reporting Serious Unanticipated Adverse Events for Drugs and Devices". Unless stated otherwise in the protocol, all SAEs, expected or unexpected, must be reported to the IND Office, regardless of attribution (within 5 working days of knowledge of the event).
- All life-threatening or fatal events, that are unexpected, and related to the study drug, must have a written report submitted within 24 hours (next working day) of knowledge of the event to the Safety Project Manager in the IND Office.
- Unless otherwise noted, the electronic SAE application (eSAE) will be utilized for safety reporting to the IND Office and MDACC IRB.
- Serious adverse events will be captured from the time of the first protocol-specific intervention, until 30 days after the last dose of drug, unless the participant withdraws consent. Serious adverse events must be followed until clinical recovery is complete and laboratory tests have returned to baseline, progression of the event has stabilized, or there has been acceptable resolution of the event.
- Additionally, any serious adverse events that occur after the 30 day time period that are related to the study treatment must be reported to the IND Office. This may include the development of a secondary malignancy.

# Reporting to FDA:

• Serious adverse events will be forwarded to FDA by the IND Sponsor (Safety Project Manager IND Office) according to 21 CFR 312.32.

It is the responsibility of the PI and the research team to ensure serious adverse events are reported according to the Code of Federal Regulations, Good Clinical Practices, the protocol guidelines, the sponsor's guidelines, and Institutional Review Board policy.

## 10.2 Data Collection

All patients who meet eligibility criteria and are enrolled in this trial will be registered in Clinical Oncology Research Database (CORe) at the University of Texas MD Anderson Cancer Center at Houston. Data will be collected and stored in the MD Anderson Protocol Data Management System (PDMS). Only adverse events related to the study drug will be captured in PDMS. Data from the MDASI and patient satisfaction survey will be stored in a Microsoft Access database that will be created and managed by [name] group.

### Data Protection and Confidentiality

All patients who meet eligibility criteria and are enrolled in this trial will be registered in CORe at the University of Texas MD Anderson Cancer Center at Houston. All protocol participants must be registered in the CORE. The date in the current informed consent document is displayed to ensure only the most current IRB approved version is used. Consent date, registration date, off study date, and evaluability data are required for all registrants.

The principal investigator agrees to keep all information and results concerning the study confidential. The confidentiality obligation applies to all personnel involved with this clinical trial. The Investigator must ensure that each participant's anonymity will be maintained in accordance with applicable laws. The principal investigator should keep a separate log of ID numbers, names and addresses. Documents that contain the names associated with these ID numbers (e.g., written consent/assent forms), should be maintained by the Investigator in strict confidence except to the extent necessary to allow auditing by regulatory authorities, auditing or monitoring by the IRB.

The Principal Investigator shall obtain all such permissions and authorizations as may be necessary or desirable to allow the collection and use of information protected under federal privacy laws and state privacy laws, including permission/authorization for monitoring and analysis (including re-analysis in combination with results of other studies), for regulatory submission purposes and for applicable reporting (if any).

### 10.3 Investigator Reporting Responsibilities

The conduct of the study will comply with all FDA safety reporting requirements. The Investigator or physician designee is responsible for verifying and providing source documentation for all adverse events and assigning the attribution for each event for all subjects enrolled on the trial

# IND Annual Reports

If the FDA has granted an IND number, it is a requirement of 21 CFR 312.33, that an annual report is provided to the FDA within 60-days of the IND anniversary date. 21 CRF 312.33 provides the data elements that are to be submitted in the report. The Annual Report should be filed in the study's Regulatory Binder.

All adverse experience reports must include the patient number, age, sex, weight, severity of reaction (mild, moderate, severe), relationship to drug (probably related, unknown relationship, definitely not related), date and time of administration of test medications and all concomitant medications, and medical treatment provided. The investigator is responsible for evaluating all adverse events to determine whether criteria for "serious" and as defined above are present.

# 11.0 Study Monitoring

This study will be monitored by the MD Anderson IND Office and a protocol-specific monitoring plan will be followed.

Regulatory monitoring will be provided by the principal investigator, the Institutional Review Board, and the Data Safety and Monitoring Board (DSMB).

# 12.0 Statistical Considerations

[name] (Professor, Department of Biostatistics) will perform all statistical analyses.

# 12.1 Study Objectives

### **Primary Objectives:**

• To determine whether glutamine decreases the severity of mucositis in patients on an mTOR inhibitor-based regimen or esophagitis in patients receiving radiation to the esophagus.

### Secondary Objectives:

- To assess whether glutamine regimen improves quality of life (QOL) in patients during mTOR inhibitor containing regimen and esophagitis during radiation to esophagus.
- To assess whether glutamine improves other measures of mucositis/esophagitis including incidence of any mucositis/esophagitis, incidence of grade 3 or higher mucositis/esophagitis, duration of mucositis/esophagitis, delay in onset of mucositis/esophagitis, and interruption of cancer treatment due to mucositis/esophagitis.

- To assess whether glutamine affects weight loss after six months of treatment for mTOR inhibitor patients and after completion of radiation therapy for esophagus radiation patients.
- To assess toxicity profile of glutamine.
- To assess whether glutamine affects muscle breakdown.

# 12.2 Study Endpoints

# **Primary Endpoints**

• For mTOR inhibitor patients, the severity of oral mucositis will be taken as the maximum grade observed during the 6-month study period. For esophagus radiation patients, the severity of esophagitis will be taken as the highest grade observed by week six.

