# 4.0 Patient Eligibility

# 4.1 Inclusion Criteria

- Patients who will be initiating therapy with any investigator-initiated mTOR inhibitor based therapy in the Department of Investigational Cancer Therapeutics (Phase I Program) or initiating radiation therapy to the esophagus.
- For the esophagitis arm, any patient with thoracic malignancies, which will receive radiation alone or concurrent chemo/radiation. Radiation dose must be ≥ 45 Gy. For the esophagitis arm, induction chemotherapy is allowed.
- Ability to understand and the willingness to sign a written informed consent. A signed informed consent must be obtained prior to any study specific procedures.
- 4) Patients must be >/= 17 years of age.
- 5) Women of child-bearing potential MUST have a negative serum or urine pregnancy test unless prior hysterectomy or menopause (defined as 12 consecutive months without menstrual activity). Patients should not become pregnant or breastfeed while on this study. Sexually active patients must agree to use contraception prior to study entry, for the duration of study participation, and for 30 days after the last dose.

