# 4.2 Exclusion Criteria

1) Patients currently receiving therapy for mucositis.

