# 5.1.2 Radiation to the Esophagus

Radiation must be  $\geq$ 45 Gy delivered alone or with concurrent chemotherapy. The type of concurrent chemo will be determined by the treating physician. For the esophagitis arm, induction chemotherapy is allowed. XRT must be given using

conventional daily fraction dose from 180-240 cGy per day. Radiation technique may include: 3D conformal, IMRT, and or protons. Glutamine will start on the first day of radiation, or within 10 days of the start of radiation and will be continued for 4 weeks after the last day of radiation. Radiation will be given daily (Monday through Friday) for 5 days per week. The number of weeks of radiation therapy will be determined by the treating physician. The end of treatment week will vary based on the number of weeks of radiation that the patient receives.

[figure not shown]

Figure 3. Treatment Regimen (Schema)

For patients who will receive mTOR inhibitor based therapy: the patients will be randomized to receive either placebo or Glutamine beginning on Day 1 of an mTOR inhibitor based therapy.

**For patients who will receive radiation to the esophagus:** the patients will be randomized to receive either placebo or Glutamine beginning on Day 1 of radiation treatment, or within 10 days of the start of radiation.

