# Secondary Endpoints

- For mTOR inhibitor patients, oral mucositis grade will be assessed at the following times: baseline, weekly during Cycle 1, and Day 1 of Cycle 2 and beyond, and end of study. For esophagus radiation patients, esophagitis grade will be assessed at the following times: baseline, weekly during radiation, end of treatment (or final week of radiation treatment based on number of weeks of radiation), and 1 month and 6 months post radiation therapy.
- For mTOR inhibitor patients, QOL will be assessed by MDASI-HN at the following times: baseline, Day 15 of Cycle 1, Day 1 of Cycles 2 and beyond, end of study, and 3 months and 6 months post end of treatment. For esophagus radiation patients, QOL will be assessed by MDASI-HN at the following times: baseline, Weeks 3, 5, and 7 of radiation, end of treatment (or final week of radiation treatment based on number of weeks of radiation), 1 month, 3 months, and 6 months post radiation therapy. For mTOR inhibitor patients, Patient Satisfaction with Study Medication will be assessed at Day 1 of Cycles 2 and beyond. For esophagus radiation patients, Patient Satisfaction with Study Medication will be assessed at Weeks 3, 5, and 7, end of treatment (or final week of radiation treatment based on number of weeks of radiation treatment based on number set as a Day 1 of Cycles 2 and beyond. For esophagus radiation patients, Patient Satisfaction with Study Medication will be assessed at Weeks 3, 5, and 7, end of treatment (or final week of radiation treatment based on number of weeks of radiation), and 1 month post radiation therapy.
- For mTOR inhibitor patients, body weight will be assessed at the following times baseline, weekly during Cycle 1, and Day 1 of Cycle 2 and beyond, and end of study. For esophagus radiation patients, body weight will be assessed at the following times: baseline, weekly during radiation, 1 month and 6 months post radiation therapy.
- For esophagus radiation patients, muscle breakdown will be assessed at baseline, weekly during radiation, 1 month and 6 months post radiation therapy.

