### 12.4 Statistical Analysis Plan

Note: Analyses will be performed separately for patients treated with mTOR inhibitors and patients with esophagus radiation.

For the primary objective, we will use the Wilcoxon rank sum test to compare the ordered categories of mucositis/esophagitis severity between treatment arms. A patient must complete at least 60% of the planned doses of placebo or glutamine to be considered evaluable in the statistical analysis. As a sensitivity analysis for the appropriateness of 60% dosing cut-off, we will analyze the outcome according to the proportion of drug taken. The proportional of drug taken will be computed as the ratio of number of doses taken to the total number of doses prescribed. For the mTOR inhibitor group, the denominator will reflect the total time that each patient is on the study. For the esophagus radiation group, the denominator will reflect the total number of doses that are prescribed during the delivery of radiation.

For the secondary objectives/endpoints, we will compare between treatment arms (1) the trajectories of the mucositis/esophagitis scores over time using linear mixed effects; (2) the proportion of patients developing mucositis/esophagitis using a Pearson chi-squared test; (3) the proportion of patients developing grade 3 or higher mucositis/esophagitis using a Pearson chi-squared test; (4) the duration of mucositis/esophagitis using the Wilcoxon rank sum test; (5) the time to develop mucositis/esophagitis using Kaplan-Meier estimates and the log rank test (due to right censoring in patients not developing mucositis/esophagitis); (6) the proportion of patients having treatment interruptions using a Pearson chi-squared test; (7) the

weight change using the Wilcoxon rank sum test; and (8) the QOL survey scores using the Wilcoxon rank sum test.

For the secondary objective of describing the toxicity profile, descriptive statistics will be provided on the grade and type of toxicity by treatment arm.

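### The primary maximum grade ignores the grade at entry, so toxicity already present can set a floor that dilutes the treatment effect; the screening grade is collected but not used.

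*Combined protocol and SAP*

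**What the plan says.** Section 12.2 defines the primary endpoint for the radiation cohort: "the severity of esophagitis will be taken as the highest grade observed by week six". For the mTOR cohort, "the severity of oral mucositis will be taken as the maximum grade observed during the 6-month study period". Neither sentence gives a starting point or mentions the grade at entry.

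Section 4.2 has one exclusion: "Patients currently receiving therapy for mucositis". Section 4.1 opens the radiation cohort to "any patient with thoracic malignancies, which will receive radiation alone or concurrent chemo/radiation", and induction chemotherapy is allowed. Section 2.1.2 names esophageal cancer among the diseases treated. In section 5.1.2, "Glutamine will start on the first day of radiation, or within 10 days of the start of radiation".

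The grade at entry is recorded. Both study calendars (6.1 and 6.2) show grading at screening, and section 12.2 lists it for the radiation cohort: "esophagitis grade will be assessed at the following times: baseline, weekly during radiation".

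Section 12.4 compares maximum grades with an unstratified Wilcoxon rank sum test. It compares "the proportion of patients developing mucositis/esophagitis using a Pearson chi-squared test", treats grade 3 or higher in the same way, and compares time to onset with a log rank test. None of these is said to use the screening grade. Randomization (12.5) is stratified by prior mucositis and prior head and neck radiation (mTOR) or by esophageal volume receiving 40 Gy (radiation), and not by current grade.

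**The concern.** A maximum can only rise. If a patient enters at grade 2 and stays there, the score is at least 2 however well glutamine works. If the patient enters at grade 3, the score carries almost no information about treatment. Such patients are plausible in the radiation cohort. Section 5.3.3 gives dysphagia as an example of what is evaluated as esophagitis, and section 9.0 ties grades 2 and 3 to altered swallowing. Section 9.0 rules out nausea as the reason for a feeding tube but does not mention tumour obstruction. Because study drug may start up to 10 days into radiation, a grade that arises before the first dose can count too.

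At stake is the power of a cohort planned at 81% with 40 patients per arm, which leaves little margin. There is also a smaller issue of definition. Incidence and onset have no stated at-risk set, so that choice could be made after the data are seen.

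**Working it through.** **Inputs (section 12.3).** Grades 0-1 / 2 / 3. Radiation: control 26/37/37%, glutamine 50/38/12%, 40 per arm, stated power 81%. mTOR: control 69/22/9%, glutamine 95/5/0%, 50 per arm, stated power 94%. Two-sided 5%, Wilcoxon rank sum.

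**Step 1: reproduce the plan's power (radiation).** Let θ = P(control grade < glutamine grade) + ½P(equal).

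- θ = 0.26×0.50 + 0.37×0.12 + ½(0.26×0.50 + 0.37×0.38 + 0.37×0.12) = 0.1300 + 0.0444 + 0.1575 = 0.3319.
- The pooled shares are 0.38, 0.375 and 0.245, so the tie factor is 1 − Σp³ = 0.8777. Null SE = √[0.8777 × 81/(12×40²)] = 0.0608.
- SE under the alternative = √[(0.0730 + 0.0532)/40] = 0.0562.
- Power = Φ[(0.1681 − 1.96×0.0608)/0.0562] = 80.8%. Simulation gives 81%.

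The same method gives 94.1% for mTOR. Simulation gives 96% there, and the mTOR losses below are measured from that figure. The plan's arithmetic is sound.

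**Step 2: add an entry floor.** Assume that a share f of each arm enters at grade 2 or 3, that this is independent of the treatment-caused grade, and that the final score is the higher of the two. With entry grades 2:3 at 70:30, the shares (p₁, p₂, p₃) become:

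- p₁′ = (1 − f)p₁
- p₂′ = (1 − 0.3f)p₂ + 0.7f·p₁
- p₃′ = p₃ + 0.3f(1 − p₃)

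At f = 10% the control arm is 23.4/37.7/38.9% and the glutamine arm 45.0/40.4/14.6%.

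**Step 3: simulated power of the test as written (tie-corrected).**

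| Radiation, 40 per arm | f = 0 | 10% | 20% | 30% |
|---|---|---|---|---|
| Entry grades 2:3 at 70:30 | 81% | 76% | 71% | 66% |
| All enter at grade 2 | 81% | 79% | 77% | 76% |
| All enter at grade 3 | 81% | 69% | 57% | 45% |

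| mTOR, 50 per arm | f = 0 | 5% | 10% |
|---|---|---|---|
| All enter at grade 2 | 96% | about 90% | 82% |

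The mTOR cohort is sensitive to small shares because its target glutamine arm is 95% grade 0-1.

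**Step 4: type I error.** With both arms given the control distribution and the same entry shares, the test as written rejects in 4.9 to 5.1% of simulated trials.

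**Step 5: effect of stratifying by screening grade (0-1 v 2 or more, van Elteren weights).** Radiation at 70:30: 76% rises to 78% (f = 10%) and 71% to about 73 to 74% (f = 20%). mTOR at a 10% grade 2 share: 82% rises to 95%. Type I error stays at about 5%.

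**The case against.** Several points on the other side stand.

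- **The plan is silent on incidence and onset.** A reader might infer that a patient already graded at entry is an event at time zero. No section says so. Section 12.4 speaks of patients *developing* toxicity, and sections 1.2 and 12.1 of a delay in onset, which suggests new events. What is missing is an at-risk set.
- **Tumour dysphagia is not scored by rule.** Section 9.0 defines esophagitis as inflammation of the esophageal wall, ties some grades to starting a medication, and provides for grader training. Mis-scoring is possible, because swallowing symptoms are the working signs and section 5.2 allows interview or phone assessment. The plan does not prescribe it.
- **No systematic bias.** A reader might infer that a chance imbalance in entry grade biases the primary result. Under blinded randomization an imbalance is random error, and step 4 shows that the type I error holds.
- **Scores are not identical across arms.** Grade 2 entrants can still reach grade 3, which glutamine might prevent. That is why the all-grade-2 row loses little.
- **The mucositis half is narrower.** Treated mucositis is excluded, and the mTOR cohort is stratified by prior mucositis, though not by current grade.
- **The shares are assumed.** If the published 26/37/37% already includes symptoms present at entry, step 2 counts part of the dilution twice. The documents do not settle this.

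None of this supplies a baseline reference for the primary endpoint or a use for the screening grade in its test.

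**Conclusion.** The point holds as a gap in endpoint definition and analysis that costs power and precision. The sample-size calculation is not in error and the comparison stays valid. The size depends on the unknown share and severity of toxicity at entry. In the radiation cohort the loss at a 10% share is about 2 points if all enter at grade 2, 5 points at 70:30 and 12 points if all enter at grade 3. In the mTOR cohort it is about 6 points at a 5% grade 2 share and 14 points at 10%. All figures assume equal shares in both arms, independence of entry and treatment-caused grade, and section 12.3 distributions that are free of entry symptoms. Claims of a biased result, or of a plan that deliberately counts entry grades as new events, go beyond the documents.

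**What to change.** In section 12.4:

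1. Keep the maximum grade as the primary score, but stratify the Wilcoxon test (van Elteren) by screening grade, 0-1 v 2 or more, in both cohorts.
2. For the proportion developing toxicity and the time to develop it, restrict the at-risk set to patients at screening grade 0.
3. For grade 3 or higher, restrict it to patients below grade 3 at screening.

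**Cost.** Only wording changes, because the screening grade is already collected. The secondary comparisons lose the patients already graded at entry. In the radiation cohort the stratified test recovers only part of the lost power. It also does not address a grade that first appears between the start of radiation and the first dose.

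**A remedy to avoid.** Counting a grade only if it exceeds the screening grade looks natural but works poorly. A patient at grade 2 throughout would rank better than one who goes from 0 to 1, and a grade 3 entrant would almost never count in either arm. Rescoring alone moves radiation power only from 75.8% to 76.4% at a 10% share and from 70.8% to 71.7% at 20% (70:30). No change to eligibility is needed for the analysis changes above.
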